Positron emission tomography (PET) is a molecular imaging modality that can probe various aspects of tumor function and biology using a variety of radiolabeled imaging agents (“tracers”). Oncologic PET imaging has seen a dramatic rise in clinical utilization over the past decade for cancer detection, staging, and evaluating residual or recurrent disease following therapy. These clinical scans use the FDA approved PET radiopharmaceutical [18F]fluoro-2-deoxy-D-glucose (FDG), which accumulates in cells in proportion to GLUT transporter and hexokinase activity. FDG thus provides a measure of tissue glucose metabolism. On May 27, 2016 [18F] anti-FACBC ([18F]Fluciclovine) with the brand name of Axumin was approved for detection of recurrent prostate cancer (Axumin 2016). ([18F]Fluciclovine is a synthetic L-leucine analogue that is transported into cells but is not incorporated into proteins. Prostate cancer has upregulated amino acid utilization and thus increased [18F]Fluciclovine uptake. [18F]Fluciclovine provides a measure of tumor growth related to amino acid transport and utilization (Shoup and Goodman, 1999, Akhurst et al., 2006, Meirelles et al., 2006, Oka et al., 2007, Yu 2009, Yu 2010, Oka et al., 2012).

The patients will be hormone naïve and have 5 or fewer bone lesions and have no visceral metastatic disease. Treatment will include systemic Radium-223(6 possible treatments over approximately 6 months) and hypofractionated radiotherapy to oligometastatic sites. Certain patients may have progressive disease as determined on the primary protocol and will not receive additional Radium-223 treatments but will remain on the trial (IRB #102312).

These preliminary and exploratory data will provide information regarding visual and semi-quantitative [18F]Fluciclovine uptake and correlate these variables with changes in uptake on standard 99mTc-MDP bone scintigraphy and CT imaging. This unique situation will allow us to obtain an initial experience on the performance and correlation of [18F]Fluciclovine bone uptake in various metastatic subtypes (lytic, blastic, marrow, mixed) compared to standard imaging tests.

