The hypothesis of this exploratory clinical trial in patients with prostate cancer metastatic to bone is that [18F]Fluciclovine-PET/CT uptake will correlate with the type of bone metastasis present (blastic, lytic, marrow, mixed) as has been seen in pre-clinical animal models. It is expected that lytic and marrow foci will exhibit the greatest [18F]Fluciclovine-PET/CT uptake.

The primary exploratory objectives of the study are:

- Abnormal [18F]Fluciclovine uptake on visual assessment will differ by the type of metastatic lesion present (blastic, lytic, marrow, mixed).
- SUVmax and SUVmean on [18F]Fluciclovine-PET/CT imaging will differ by the type of metastatic lesion present (blastic, lytic, marrow, mixed).

Secondary Exploratory Objectives are outlined below

- Determine if a 25% or greater reduction in aveSUVmax or aveSUVmean on [18F]Fluciclovine-PET/CT imaging after completion of all radiation therapy will be predictive of increased time to biochemical failure.
- Determine the correlation between the number of lesions, their visual uptake, and semi-quantitative uptake on 99mTc-MDP bone scintigraphy and [18F]Fluciclovine- PET/CT at baseline
- Determine the correlation between the number of lesions, their visual uptake, and semi-quantitative uptake on 99mTc-MDP bone scintigraphy and [18F]Fluciclovine- PET/CT after 3 and 6 cycles of treatment.

Study Population

Age of Participants: 18+

Sample Size:

At Utah: 15
All Centers: 18

Inclusion Criteria:

- Enrollment on IRB #102312 (A Phase 2 Study of Radium-223 and Radiotherapy in Hormone-Naïve Men with Oligometastatic Prostate Cancer to Bone).
- Patients must document their willingness to be followed for up to 24 months after recruitment by signing informed consent documenting their agreement to allow access to the data obtained on IRB #102312 and information and data entered into a research database.
- All patients, or their legal guardians, must sign a written informed consent and HIPAA authorization in accordance with institutional guidelines.

Exclusion Criteria:

- Patients with known allergic or hypersensitivity reactions to previously administered radiopharmaceuticals. Patients with significant drug or other allergies or autoimmune diseases may be enrolled at the Investigator's discretion.

- Patients who require monitored anesthesia for PET scanning.
- Patients who are too claustrophobic to undergo PET scanning.

Design

Prospective Biomedical Intervention or Experiment
Open Label Trial

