Patients who sign from a remote location will return their original ICF to the study team. If the original is unavailable, the patients will be asked to and sign another original in the presence of the study team.

Procedures:

As described in the consent form:

Your participation for this study will consist of a screening visit (today), and up to three additional imaging sessions: 1) prior to any tumor-directed radiation therapy; 2) between months 3 and 4 of treatment or follow up; and 3) at approximately 6-7 months.

Screening Visit

Before the study starts, you will be asked to sign this informed consent form, and a member of the Study Staff will ask you about your general health history, treatments you have had for your prostate cancer, if you take any over-the-counter or prescription medicines, vitamins, or herbs, and if you have any drug allergies.

The Study Staff will also record information from your medical records including previous blood test results, procedures, treatments, and plans for your prostate cancer treatment.

If you agree to participate in the study and you qualify for the study, then you will be scheduled for your first scan before you receive any treatment with Radium 223. The Study Staff will tell you when and where the PET/CT scan will be performed.

Day of Imaging Session 1: Baseline

Before the dosing of [¹⁸F]Fluciclovine and the PET/CT scan, a member of the Study Staff will ask you questions about any changes to your general health and medications since your screening visit.

The following tests will be performed before dosing:

- Measurement of your height and weight
- Assessment of vital signs (blood pressure, heart rate, and temperature)

PET/CT Scan [¹⁸F]Fluciclovine

The Study Staff will place an IV catheter (long, thin tube) into a vein in your arm. You will receive the [¹⁸F]Fluciclovine injection through the catheter in your arm immediately before the scan. During the scan, you will lie on your back on the scanning bed. The bed will move slowly through the PET/CT scanner. The CT portion of the scan usually takes about 1 minute, and sends X-rays through your body that are measured by the CT camera. The PET portion of the scan begins immediately after the CT scan and will last about 60 minutes.

You should not exercise the day before the scan and until the scan is finished. Do not eat or drink for at least 8 hours before the scan; sips of water to take medication are permitted.

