This entire visit should require approximately 2 to 3 hours of your time.

Immediately Following Each Scan

Immediately following the scan, a member of the study staff will obtain your vital signs, including your blood pressure, heart rate, and temperature.

Day after Each Scan (or up to 3 days after scan)

You will be contacted by a member of the Study Staff to discuss whether you have had any side effects within the 24 hours after you received the [¹⁸F]Fluciclovine.

Day of Imaging Sessions 2 and 3: During Treatment and After Treatment with Radium 223

Similarly, prior to imaging sessions 2 and 3, a member of the Study Staff will ask you questions about any changes to your general health and medications since your screening visit.

The following tests will be performed before dosing:

- Measurement of your height and weight
- Assessment of vital signs (blood pressure, heart rate, and temperature)

PET/CT Scan [¹⁸F]Fluciclovine

The process of placing an IV catheter, receiving the [¹⁸F]Fluciclovine injection, and the approximate 60 minute scan will remain the same as described in the baseline imaging. You should not exercise the day before the scan and until the scan is finished. Do not eat or drink for at least 8 hours before the scan; sips of water to take medications are permitted.

This entire visit should require approximately 2 to 3 hours of your time.

Immediately Following Each Scan

Immediately following each scan, a member of the study staff will obtain your vital signs, including your blood pressure, heart rate, and temperature.

Day after Each Scan (or up to 3 days after scan)

You will be contacted by a member of the Study Staff to discuss whether you have had any side effects within the 24 hours after you received the [¹⁸F]Fluciclovine.

Follow-up

You will be followed up for 24 months after you sign the consent form. This will be done by reviewing your medical records.

Procedures performed for research purposes only:

Statistical Methods, Data Analysis and Interpretation

Data Analysis

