Qualitative and Visual Assessment. The images for the standard ^{99m}Tc -MDP bone scintigraphy and the $[^{18}\text{F}]\text{Fluciclovine}$ -PET/CT will be visually assessed for any artifacts. The images will then be independently scored as described earlier for each imaging modality based on the level of uptake and confidence of tumor presence. The concordance of the agreement will be assessed and compared with the CT determination of metastasis type (lytic, blastic, mixed). Data will then be assessed and tabulated on a lesion by lesion basis for all of the imaging modalities over time as to the presence and the confidence of metastatic prostate cancer. Bland-Altman plots will be prepared.

Semi- and Fully-Quantitative Assessments.

The primary analysis of SUV_{max} and SUV_{mean} will be *t*-tests comparing the osteoblastic and osteolytic lesions. An additional analysis of the primary objective will be one way ANOVA with Tukey's post hoc analysis comparing all four lesion types (osteoblastic, osteolytic, marrow and mixed). As a secondary sensitivity analysis mixed effects models with a fixed effect for lesion type and a random patient effect will also be fit.

Spearman correlation of lesion uptake on ^{99m}Tc -MDP bone scintigraphy and $[^{18}\text{F}]\text{Fluciclovine}$ -PET/CT at baseline and after 3 cycles of Radium 223 will be calculated. The number of lesions identified by ^{99m}Tc -MDP bone scintigraphy alone, $[^{18}\text{F}]\text{Fluciclovine}$ -PET/CT alone, and both ^{99m}Tc -MDP bone scintigraphy and $[^{18}\text{F}]\text{Fluciclovine}$ -PET/CT will be tabulated.

Spearman correlation of lesion uptake on ^{99m}Tc -MDP bone scintigraphy and $[^{18}\text{F}]\text{Fluciclovine}$ -PET/CT at baseline and after 6 cycles will be calculated (6-7 months for those individuals who progressed). The number of lesions identified by ^{99m}Tc -MDP bone scintigraphy alone, $[^{18}\text{F}]\text{Fluciclovine}$ -PET/CT alone, and both ^{99m}Tc -MDP bone scintigraphy and $[^{18}\text{F}]\text{Fluciclovine}$ -PET/CT will be tabulated.

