Time to biochemical failure will be analyzed using standard survival analysis methods. Two binary variables will be constructed, by dividing the cohort into those that did and did not achieve a 25% or greater reduction in ave SUV_{max} or ave SUV_{mean} on $[^{18}\text{F}]\text{Fluciclovine}$ -PET/CT imaging after completion of all radiation therapy. Here ave SUV_{max} and ave SUV_{mean} are defined as the average SUV_{max} and the average SUV_{mean} across all identified lesions. Kaplan-Meier methods will be used for plotting and log rank tests will be used to

determine whether either of these binary variable is predictive of increased time to biochemical failure.

Justification of Sample Size

(Sample size calculations were prepared by [name]. of the HCI Biostatistics Resource)

This is a companion study to IRB #102312 (A Phase 2 Study of Radium-223 and Radiotherapy in Hormone-Naïve Men with Oligometastatic Prostate Cancer to Bone). The primary outcome of IRB #102312 is progression require ADT therapy. The planned accrual time is 12-24 months with an additional 24 months of follow up. We provide sample size justifications for the primary objective.

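### Men are grouped by SUV fall on a PET taken at about 6-7 months, but time to biochemical failure is compared by log-rank with no landmark or time origin, so a failure can precede its own predictor

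*Combined protocol and SAP*

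**What the plan says.** The Secondary Exploratory Objectives ask whether a fall of at least 25% in aveSUVmax or aveSUVmean "after completion of all radiation therapy will be predictive of increased time to biochemical failure". The matching analysis, at the end of the Data Analysis text, builds two binary variables by "dividing the cohort into those that did and did not achieve a 25% or greater reduction in ave" SUVmax or SUVmean. The average is taken "across all identified lesions". On method it says "Time to biochemical failure will be analyzed using standard survival analysis methods", and then names Kaplan-Meier plots and log-rank tests.

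On timing, Purpose and Objectives describes up to six Radium-223 treatments over about six months. Procedures lists three imaging sessions: one before tumor-directed radiation, one between months 3 and 4, and the last "3) at approximately 6-7 months". The follow-up clock is given in the Follow-up paragraph: "You will be followed up for 24 months after you sign the consent form".

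On men who worsen early, Purpose and Objectives says that those with progressive disease "will not receive additional Radium-223 treatments but will remain on the trial". The Spearman paragraph for the six-cycle assessment gives its timing as "6-7 months for those individuals who progressed".

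The document does not define biochemical failure, set a time origin for it, name a landmark, or say how to treat men who fail before the scan or miss it.

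**The concern.** The responder label is a post-baseline measurement. A man cannot be classified until his post-treatment scan, yet nothing stops his time to failure from being counted from consent or baseline. If it is, the comparison includes months in which no one's group was known, and failures in those months are assigned to a group by a scan done afterwards.

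The plan makes this order of events possible. Men whose disease has progressed stay in the cohort and are still imaged at 6-7 months. Progression is not the same as biochemical failure, so this does not show how often biochemical failure will come first. It does show that early worsening is expected and does not remove a man from the analysis.

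The direction of the bias depends on how early failures score on the later scan. If they show a 25% fall less often than other men, the comparison favors responders. If they show it more often, the comparison runs against responders. If equally often, there is essentially no bias in the test, but a scan done after failure still cannot predict that failure. The plan as written cannot separate these cases from a true association. This is the only listed objective that links the PET result to a later patient outcome.

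**Working it through.** The plan states no event count, hazard ratio, significance level or power for this comparison, so there is no figure of its own to reproduce. The check has two parts.

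**1. How many failures could precede the scan?**

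From the document: N = 18 (All Centers and the sample size justification); last scan at 6-7 months, taken as 6.5; follow-up 24 months. Assumed: exponential time to failure with median M from 12 to 36 months, and clock started at baseline.

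- Failures before the scan = 18 × (1 − 2^(−6.5/M))
- Failures by 24 months = 18 × (1 − 2^(−24/M))

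For M = 12: 18 × (1 − 0.687) = 5.6 before the scan, and 18 × (1 − 0.25) = 13.5 by 24 months. For M = 36: 18 × (1 − 0.882) = 2.1, and 18 × (1 − 0.630) = 6.7.

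| Median (months) | Fail before scan | Fail by 24 months | Share before scan |
|---|---|---|---|
| 12 | 5.6 | 13.5 | 42% |
| 18 | 4.0 | 10.9 | 37% |
| 24 | 3.1 | 9.0 | 34% |
| 36 | 2.1 | 6.7 | 32% |

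Under these assumptions, about a third or more of all observed failures come before the predictor is measured.

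**2. What does that do to the log-rank test?**

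Simulation, 10,000 runs per setting, with the inputs above. A man failure-free at the scan is a responder with probability p. A man who failed earlier is a responder with probability p × q. After the scan, response and failure are unrelated. The test is two-sided at a nominal 5%, which is an assumption because the plan gives no level for this test. The Monte Carlo standard error near 5% is √(0.05 × 0.95 / 10,000) ≈ 0.2 percentage points.

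Rejection rate of the log-rank on the whole cohort from baseline, for medians 12 / 18 / 24 / 36 months:

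| Early failures respond | p = 0.50 | p = 0.35 |
|---|---|---|
| never (q = 0) | 0.220 / 0.169 / 0.140 / 0.099 | 0.111 / 0.076 / 0.067 / 0.053 |
| half as often (q = 0.5) | 0.098 / 0.088 / 0.077 / 0.063 | 0.059 / 0.059 / 0.057 / 0.042 |
| equally often (q = 1) | 0.060 / 0.060 / 0.056 / 0.049 | 0.067 / 0.055 / 0.056 / 0.052 |
| twice as often (q = 2) | 0.218 / 0.164 / 0.138 / 0.103 | 0.174 / 0.140 / 0.128 / 0.098 |

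At p = 0.50, q = 2 means that every early failure is a responder, and nearly all those rejections go against responders. With the clock started at the scan and only failure-free men included, the rate is 0.040-0.072 over all settings; the small excess over 5% is small-sample error.

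**The case against.** - **Mechanism.** In the classic form of guarantee-time bias, failing early prevents a man from being classed as a responder. Here men who progress are still to be scanned, so early failures need not default to non-response. This stands: the bias is conditional and can run either way. The order problem does not depend on it.
- **The simulated null.** Where q differs from 1, early failure and SUV response really are associated in the simulated data, so the log-rank is detecting something. That is true, but the association runs backward in time, and the stated aim is prediction.
- **Inputs.** All the driving rates are assumed. With q = 1 the test is close to nominal, and with 35% responders and q = 0.5 it is 4-6%. The larger figures need strong dependence between early failure and response. This also stands.
- **Which scan.** The analysis text does not name session 3. For a man whose Radium-223 stops early, the month 3-4 scan might qualify. The label is post-baseline either way, and the ambiguity is a reason to name the scan.
- **Unseen documents.** The text refers to a full protocol and relies on the parent study, either of which may define the endpoint and its origin. If so, a citation closes part of the gap.
- **Weight.** This is one unpowered exploratory comparison in 18 men. That limits the importance of the point but does not make the stated method suit its question.

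**Conclusion.** The concern holds. Followed as written, the plan allows biochemical failures that occurred before the post-therapy scan to count toward a claim that the scan predicts failure. Under the assumed median of 12-36 months, that is roughly 5.6 to 2.1 of 18 men. The effect on the log-rank ranges from none, when response is unrelated to early failure, to about 22% rejection at a nominal 5%, in either direction, when early failures all fall on one side and half the men respond. These rates illustrate a range and do not estimate what this trial will see. What needs no assumption is that the grouping is post-baseline and that no origin, landmark or rule for earlier failures is given. The point is confined to this secondary exploratory comparison; the primary lesion-type analysis and the sample size do not depend on it.

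**What to change.** In the time-to-biochemical-failure paragraph:

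1. Name the qualifying scan, including for men whose Radium-223 stops early.
2. Start the clock at that scan, or at a fixed landmark of about 7 months. Include only men who have the scan and are still free of biochemical failure.
3. Report separately the number of men who failed before the scan or had no scan, with the SUV change where it was measured.
4. Define biochemical failure and its time origin, or cite where the full protocol or parent study does so.

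Fitting SUV response as a time-dependent covariate is an acceptable alternative to step 2.

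The change is wording only, with no added scans or visits. The cost is information: expected events fall from 13.5 to about 7.9 (median 12 months) or from 6.7 to about 4.5 (median 36 months). With hazard ratio = exp(−(1.96 + 0.84)/√(events/4)), for equal groups, two-sided 5% and 80% power, the detectable hazard ratio moves from 0.22 to 0.14, or from 0.11 to 0.07. Neither version supports firm inference, so results should be described as exploratory in both.

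A separate clarification, which carries no weight in the conclusion: the plan does not say at which scan the averaged lesions are identified. It should fix the baseline set, re-measure the same sites even when uptake has fallen to background, and report new lesions separately. As an invented illustration, take baseline SUVs of 12, 6 and 4 (mean 7.33) and follow-up values of 10, 1.5 and 1.2 (mean 4.23). The change is −42% over the same three sites, but 10/7.33 gives +36% if only the lesion of 10 is still counted.

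### SUV change is tested against biochemical failure only through a 25% split, with no effect estimate; a supportive Cox model on continuous change would be a cheap addition

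*Combined protocol and SAP*

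**What the plan says.** Among the secondary exploratory objectives (Purpose and Objectives), the plan aims to "Determine if a 25% or greater reduction in aveSUVmax or aveSUVmean on" fluciclovine PET/CT after all radiation therapy predicts a longer time to biochemical failure. The 25% threshold is therefore part of the stated question.

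The analysis is at the end of Data Analysis, under Semi- and Fully-Quantitative Assessments. It opens with "Time to biochemical failure will be analyzed using standard survival analysis methods" and then names the predictors: "Two binary variables will be constructed", formed by "dividing the cohort into those that did and did not achieve a 25% or greater reduction in ave" SUVmax or SUVmean, each averaged over a man's identified lesions. On method it plans Kaplan-Meier plots and log-rank tests, whose stated purpose is to "determine whether either of these binary variable is predictive of increased time to biochemical failure".

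No Cox model, hazard ratio, confidence interval or continuous form of the SUV change is specified for this endpoint. Study Population gives "All Centers: 18", and the Follow-up text says "You will be followed up for 24 months after you sign the consent form". Justification of Sample Size covers the primary objective only. No basis is given for 25%, and no expected share of men reaching it or number of biochemical failures.

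**The concern.** Cutting a measured percent change at one value treats a 26% and an 80% reduction as the same, and a 24% and a 26% reduction as different. With at most 18 men, that can cost a noticeable part of whatever graded relation exists. If the split turns out lopsided, the log-rank test has almost nothing to compare. The plan also promises only a curve and a p-value, so a reader of the results would not learn how large the association might be or how uncertain it is.

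At stake is one secondary exploratory question. It could end without a usable comparison even though percent change is on file for every man scanned at both times.

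**Working it through.** The plan states no power or event figure for this endpoint, so there is none to reproduce. From the document come the 25% cut, the two measures, the log-rank tests and the maximum of 18 men. Everything else below is an assumption.

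**1. Information kept by a split.** Assume a normal percent change and a log-linear effect on the hazard. If a proportion p falls on one side of the cut, the efficiency relative to the continuous covariate is φ(z_p)² / [p(1 − p)].

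- 50/50: 0.3989² / 0.25 = 0.64, so 18 men count as 11.5.
- 80/20: 0.2800² / 0.16 = 0.49, so 18 men count as 8.8.
- 90/10: 0.1755² / 0.09 = 0.34, so 18 men count as 6.2.

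The loss is thus 36%, 51% and 66%. Other distributions move it: for splits between 50/50 and 90/10, a uniform covariate gives 25% to 73% and a lognormal one (sigma 0.5) about 39% to 85%.

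**2. Power with 18 men.** This was simulated with 60% events (about 11) and a two-sided 0.05 level, comparing the log-rank test with the Cox score test on the continuous value. Each test has one parameter. The assumed hazard ratio is 2 per SD of change.

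| Split | Continuous | 25% split |
|---|---|---|
| 50/50 | about 53% | about 37% |
| 80/20 | about 53% | about 45% |
| 90/10 | about 53% | about 40% |

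The gap narrows at skewed splits partly because the log-rank test is then anti-conservative. With no effect it rejects about 8% of the time at 80/20 and 9% to 10% at 90/10, against just under 6% for the continuous test.

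**3. The reverse case.** If the true effect is a step at the cut (hazard ratio 4), the split wins: 58% against 42% at 50/50, and 59% against 25% at 80/20.

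**4. Near-empty groups.** If 90% of men reach 25%, the chance that 0 or 1 of 18 does not is 0.9¹⁸ + 18 × 0.1 × 0.9¹⁷ = 0.150 + 0.300 = 45%. If 80% do, it is 0.018 + 0.081 = 10%. With nobody in one group there is no test. With one man, an exact log-rank p-value cannot fall below 1/18 = 0.056.

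**5. Limits of the gain.** For 80% power at a hazard ratio of 2 per SD, the continuous model needs (1.96 + 0.84)² / (ln 2)² = 16.3, so 17 events, nearly all of the 18 men.

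**6. Multiplicity.** Two tests at 0.05, if independent, give 1 − 0.95² = 9.8% chance of a false positive. Four give 1 − 0.95⁴ = 18.5%.

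**The case against.** The strongest reply is that the plan answers the question it set. The 25% threshold is in the objective, the analysis matches it, the endpoint is exploratory, and the opening reference to standard survival methods does not rule out a Cox model. If a step at 25% is what the investigators have in mind, the binary test is also the more powerful one. All of this stands as a reason to keep the 25% test. It is no reason to omit an effect estimate or a prespecified look at the graded relation, and the general opening sentence does not prespecify either.

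A second reply is that few events argue against modelling. This does not hold here, because a Cox model with one continuous covariate has the same single parameter as a two-group log-rank test.

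Two stronger readings are tempting, and the document does not support them. A reader might infer that every metastatic site is irradiated, so nearly all men will pass 25%. The plan says only that hypofractionated radiotherapy goes to oligometastatic sites. It also expects that some men may progress and stop Radium-223, and it gives no expected response share. A lopsided split is possible but not established. A reader might also take a loss of a third to two thirds of the information as a property of the plan. That range holds only under a normal covariate, a log-linear hazard and an assumed split, none of which the document provides.

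**Conclusion.** The point holds as a modest improvement. The analysis of biochemical failure rests on one dichotomy per measure in at most 18 men and reports no effect size. Under the assumptions stated, a continuous covariate would raise power by roughly 16 points at an even split and 8 to 13 points at 80/20 to 90/10, and it would remain usable if one group were nearly empty. Under a step at 25% the advantage belongs to the planned test.

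The evidence does not support calling the 25% analysis wrong or replacing it. Power is limited either way, so the main value of the addition is an estimate with its interval. The hazard ratios, the 60% event share and the splits are all illustrative, since the document gives none of them.

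**What to change.** Keep the 25% objective, the Kaplan-Meier plots and the two log-rank tests. Add to Data Analysis, before the outcome data are examined, one supportive Cox model per measure with percent change in aveSUVmax or aveSUVmean as a continuous covariate. Report the hazard ratio per 25-point reduction with its confidence interval. Use the same men and the same time origin as the log-rank tests, and report how many men fall on each side of 25%.

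Label the two models supportive and for estimation. Otherwise the plan would have four tests each read at 0.05, with the rise in false-positive chance shown above.

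The cost is two more models and an assumed log-linear effect. No additional scans, patients or follow-up are needed.

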We focus on separate comparisons of the difference in SUV_{max} and SUV_{mean} in osteolytic vs osteoblastic lesions. Both SUV_{max} and SUV_{mean} are expected to be appreciably higher in osteolytic lesions. The data available for assessment of power is sparse. Oka reported tumor to background (T/BG) ratios of approximately 3 ± 1.0 and 4.5 ± 1.0 (mean \pm SD) for ^{14}C -fluciclovine uptake in osteoblastic and osteolytic lesions respectively in bone metastasis models in mice (Oka et al. 2017). A recent human study by Janssen provides some information that can be used in the current study to determine the sample size (Janssen et al 2017). The study assessed $[^{68}Ga]PSMA-HBED-CC$ uptake in osteolytic, osteoblastic, and bone marrow metastases in prostate cancer patients. It is expected that the $[^{68}Ga]PSMA-HBED-CC$ and $[^{18}F]Fluciclovine$ will behave similarly for the detection of bone metastases depending on the type (blastic, lytic, marrow, mixed). As reported in table 3 of that manuscript, a median SUV_{max} for $[^{68}Ga]PSMA-HBED-CC$ imaging of 10.6 ± 7.1 and 24.0 ± 19.3 in osteoblastic and osteolytic bone metastases in prostate cancer patients with at least one bone metastasis (Janssen et al 2017, The number of osteolytic and osteoblastic lesions in the study were 21/154 (13.6%) and 80/154 (51.9%) respectively, and there were approximately 5 lesions per subject (154 lesions in 30 patients).

Guided by the data in Janssen (Janssen et al., 2017) we assume:

1. 5 lesions per subject. As in Janssen (Janssen et al., 2017) uptake of lesions in the same patient is assumed to be independent.
2. A standard deviation of 14.5 for mean SUV_{max} or SUV_{mean} .
3. The proportion of osteoblastic and osteolytic lesions will be 50% and 13% respectively.
4. The use of separate two sample t - tests at the one sided 0.05 significance level for comparison of SUV_{max} and SUV_{mean} between osteoblastic and osteolytic lesions.

With these assumptions a sample size of 18 evaluable subjects will provide 80% power to detect a difference of 14.7 in mean SUV_{max} or SUV_{mean} between osteolytic and osteoblastic lesions.

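### The 80% power at 14.7 does not follow from the stated inputs, and it rests on an unexplained mean of 5 lesions per man, equal to the entry limit

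*Combined protocol and SAP*

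**What the plan says.** All references are to the combined protocol and SAP.

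*Justification of Sample Size* plans the primary comparison of uptake in osteolytic and osteoblastic lesions. Its inputs come from a cited human PSMA PET study:

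- **Lesion count:** 5 per subject, treated as independent within a man. In the source, "there were approximately 5 lesions per subject (154 lesions in 30 patients"). That cohort is described only as having uptake measured "in prostate cancer patients with at least one bone metastasis", with no upper limit mentioned.
- **Spread:** a single SD of 14.5. The source values printed in the same section are 10.6 ± 7.1 (osteoblastic) and 24.0 ± 19.3 (osteolytic).
- **Mix:** "The proportion of osteoblastic and osteolytic lesions will be 50% and 13% respectively".
- **Test:** "The use of separate two sample t - tests at the one sided 0.05 significance level".

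From these it concludes that "18 evaluable subjects will provide 80% power to detect a difference of 14.7 in mean" SUVmax or SUVmean. No other scenario is shown. Planned enrolment is the same number ("All Centers: 18").

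*Purpose and Objectives* describes the men to be imaged as hormone-naïve patients who "have 5 or fewer bone lesions and have no visceral metastatic disease".

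**The concern.** There are two separate problems in one sentence of the plan.

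First, the result is presented as following from the listed assumptions, so a reader should be able to reproduce it. It does not reproduce.

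Second, the mean of 5 lesions was carried over from a cohort with no stated cap into a population capped at 5. If the analysed lesions are those counted at entry, a mean of 5 requires every man to have exactly 5.

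This is the only planning figure for the primary comparison, and the lytic group is the scarce one: about 12 lesions at a mean of 5, about 7 at 3, and about 5 at 2. The basis matters for how a null result is read. The two source values differ by 24.0 − 10.6 = 13.4. One basis puts the 80%-power difference below that (12.0) and another puts it above (about 15.2). As written, the plan does not tell the reader which applies.

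**Working it through.** **Inputs** (all from *Justification of Sample Size*): 18 men, m = 5 lesions each, 50% blastic, 13% lytic, SD 14.5, one-sided 0.05, independent lesions.

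**1. The plan's own figure.**
- Blastic lesions: 0.50 × 18 × 5 = 45. Lytic lesions: 0.13 × 18 × 5 = 11.7.
- SE = 14.5 × √(1/45 + 1/11.7) = 4.758.
- Noncentrality at 14.7: 14.7 / 4.758 = 3.089, with df = 54.7 and critical t = 1.673.
- Power from the noncentral t = 0.920. The difference giving 80% power is 11.98.

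The stated 80% at 14.7 is therefore not reproduced. Rounding does not explain it: 11 lytic lesions give 90.8% (80% at 12.28), and 12 give 92.5% (80% at 11.86). A two-sided 0.05 test gives 85.9% (80% at 13.57). With 90 lesions, the SD would have to be 17.8 to give 80% at 14.7.

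**2. A route that does give 14.7.**
- Root mean square of the source SDs: √((7.1² + 19.3²)/2) = 14.54, which is evidently where 14.5 comes from.
- Using the two SDs separately, with 11.7 rounded down to 11 and a normal approximation: (1.645 + 0.842) × √(7.1²/45 + 19.3²/11) = 2.4865 × √(1.120 + 33.863) = 2.4865 × 5.9146 = 14.71.

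This matches the printed figure, but the plan does not state it and its second assumption contradicts it. The match also depends on the rounding: 11.7 lesions give 14.27.

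**3. The same SDs with an unequal-variance t-test.** With 45 versus 11.7 lesions:
- SE = √(1.120 + 31.837) = 5.741, approximate df = 11.5, critical t = 1.789.
- Power at 14.7 = 78%. The 80%-power difference is 15.2.

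**4. Lower mean lesion counts.** 18 evaluable men, other inputs as above. Means below 5 are assumptions; the documents give no expected mean for this population.

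| Mean lesions per man | Blastic / lytic | Common SD 14.5: 80% at | Power at 14.7 | SDs 7.1/19.3: 80% at | Power at 14.7 |
|---|---|---|---|---|---|
| 5 | 45 / 11.7 | 12.0 | 92% | 15.2 | 78% |
| 4 | 36 / 9.4 | 13.4 | 86% | 17.3 | 68% |
| 3 | 27 / 7.0 | 15.6 | 76% | 20.7 | 55% |
| 2 | 18 / 4.7 | 19.4 | 60% | 27.7 | 38% |

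The common-SD columns use the pooled t-test, and the source-SD columns use the unequal-variance t-test.

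**The case against.** The best defence is that 14.7 may be sound and only its description wrong. If the statistician used the two source SDs, the figure reflects the cited data better than 12.0 would, and the slip lies in summarising the spread as 14.5. This stands as a plausible origin, and it is why 12.0 cannot simply be substituted. It does not rescue the text, because the plan states a single SD and says the result follows from it. Nor is it the only route to about 80%. A within-patient correlation near 0.12 also gets there, but contradicts the stated independence.

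A second defence concerns the cap. The limit of five names no imaging method, and the analysis section tabulates lesions seen on fluciclovine PET/CT alone, so the analysed count could exceed the entry count. This also stands: a mean of 5 is not impossible. But the sample-size section does not give that reason. It relies only on the source cohort.

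A third is that the study is labelled exploratory and the plan admits that its power data are sparse. That limits the stakes but does not excuse a formal power statement that cannot be reproduced.

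A reader might also infer that 14.7 amounts to a hidden mean of about 3.4 lesions (about 61 in all under the common SD), so that the plan understates its sensitivity for any mean between 3.4 and 5. The documents do not support that. It holds only under the common SD. Under the source SDs, 14.7 is already slightly missed at a mean of 5.

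**Conclusion.** The concern holds in two parts. The printed power statement is inconsistent with its stated inputs: they give 92% at 14.7, or 80% at 12.0. The mean of 5 equals the entry limit and is not justified for this population, and no figure is given for a lower mean.

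The direction of the error is not settled. Under the common SD the statement is cautious at a mean of 5; under the source SDs with an unequal-variance test it is slightly optimistic (about 78%). It would be going too far to say that the trial is underpowered, or that 12.0 is the right detectable difference. Either claim needs a basis that the plan has not fixed.

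Across assumed means of 4 to 2, power at 14.7 runs from 86% to 60% on one basis and from 68% to 38% on the other. All these figures assume 18 evaluable men, independent lesions and the stated 50%/13% mix.

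**What to change.** Revise *Justification of Sample Size* as follows.

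1. State which calculation produced 14.7, and make the assumptions and the result agree. Either keep the common SD of 14.5 and report 80% power at 12.0 (92% at 14.7), or state SDs of 7.1 and 19.3 with an unequal-variance t-test and report 80% power at about 15.2 (about 78% at 14.7, using 11.7 lytic lesions).
2. Justify the mean of 5, for example by an expected yield of lesions seen on PET alone, or replace it with a mean compatible with the entry limit. The parent study's baseline lesion counts are a natural source, since every man must be enrolled there.
3. Add the rows for means of 4, 3 and 2 on the chosen basis, labelled as assumptions.

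No patients need be added and no procedures change. The cost is a rewrite of one section. If the unequal-variance basis is chosen, the analysis section, which says only that t-tests will be used, should also name that form of the test. The downside is that the restated detectable difference may be less favourable than 14.7.
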